8.6. Pregnancies

While pregnancy itself is not considered to be an AE or SAE, any pregnancy complication or elective termination of a pregnancy for medical reasons will be recorded as an AE or SAE as described in the protocol. If subjects and subjects' partner become pregnant while on the study, the information will be included in the narratives and no separate table or listing will be produced.

8.7. Clinical Laboratory Analyses

Laboratory evaluations including the analyses of Chemistry laboratory tests, Haematology laboratory tests, Urinalysis, and liver function tests will be based on GSK Core Data Standards. The details of the planned displays are in [Appendix 13: List of Data Displays](#). Summary of change from baseline by scheduled visits using mean, median, standard deviation, minimum and maximum will be provided.

Summaries of worst case grade increase from baseline grade will be provided for all the lab tests that are gradable by CTCAE v4.03. These summaries will display the number and percentage of subjects with a maximum post-baseline grade increasing from their baseline grade. Any increase in grade from baseline will be summarized along with any increase to a maximum grade of 3 and any increase to a maximum grade of 4. Missing baseline grade will be assumed as grade 0. For laboratory tests that are graded for both low and high values, summaries will be done separately and labelled by direction, e.g., sodium will be summarized as hyponatremia and hypernatremia.

For lab tests that are not gradable by CTCAE v4.03, summaries of worst case changes from baseline with respect to normal range will be generated. Decreases to low, changes to normal or no changes from baseline, and increases to high will be summarized for the worst case post-baseline. If a subject has a decrease to low and an increase to high during the same time interval, then the subject is counted in both the "Decrease to Low" categories and the "Increase to High" categories.

Separate summary tables for haematology, and chemistry laboratory tests will be produced. Liver function laboratory tests will be included with chemical chemistry.

For spot urine albumin/creatinine ratio (mg/g), a shift table from baseline to worst post-baseline will be provided.

A supporting listing of laboratory data for subjects with abnormalities of potential clinical concern will be provided. A separate listing of laboratory data with character values will also be provided.

Detailed derivation of baseline assessment is specified in [Section 5.2](#)

Unless otherwise specified, the denominator in percentage calculation at each scheduled visit will be based on the number of subjects with non-missing value at each particular visit.

8.7.1. Analyses of Liver Function Tests

Summaries of hepatobiliary laboratory events including possible Hy's law cases will be provided in addition to what has been described above.

A plot of maximum ALT vs. baseline ALT will be generated. Plots of maximum total bilirubin versus maximum ALT, maximum AST versus maximum LDH, maximum AST versus maximum Creatinine Kinase, and maximum LDH versus maximum Creatinine Kinase will be generated.

A Summary of Liver Monitoring/Stopping Event Reporting will be provided. The medical conditions data for subjects with liver stopping events will be listed. The substance use data for subjects with liver stopping events will be listed.

8.8. Other Safety Analyses

The analyses of non-laboratory safety test results including ECGs and vital signs will be based on GSK Core Data Standards, unless otherwise specified. The details of the planned displays are presented in [Appendix 13](#): List of Data Displays.

Unless otherwise specified, the denominator in percentage calculation at each scheduled visit will be based on the number of subjects with non-missing value at each particular visit.

8.8.1. Performance Status

ECOG performance status will be summarized at baseline and each post-baseline scheduled visit. Summaries will use frequency and percentage of subjects at each planned assessment time. A summary of change from baseline by scheduled visits will be performed, as well as the worst case post-baseline and the best case post-baseline changes during the study (improved, no change, deteriorated).

A supporting listing will also be provided.

8.8.2. ECG

A summary of the number and percentage of subjects who had normal and abnormal (clinically significant and not clinically significant) ECG findings will be displayed by scheduled visits as well as for the worst case post-baseline.

The QTc values based on Fridericia formula will be rounded to the integer and the values will be categorized into the following CTCAE grade and ranges: Grade 0 (<450 msec), Grade 1 (450-480 msec), Grade 2 (481-500 msec), and Grade 3 (\geq 501 msec). Summaries of grade increase will be provided. These summaries will display the number and percentage of subjects with any grade increase, increase to grade 2 and increase to grade 3 in the worst case post-baseline only.

The changes in QTc values will be categorized into the clinical concern ranges which are specific to changes in QTc: 31-60 and >60 msec. A summary of change in QTc value will

display the number and percentage of subjects with a change within each range in the worst case post-baseline only. Subjects with missing baseline values will be excluded from this summary.

A listing of QTc values of potential clinical importance will be provided

The summaries and listing of QTc will use the collected values based on Fridericia formula.

A figure plotting the baseline QTc and the worst-case post-baseline values will be produced. The figure will have reference lines at 480 and 500 msec for both the ordinate and the abscissa axes. There will be diagonal reference lines at equality (i.e. a 45 degree line), at equality plus 30 msec, and at equality plus 60 msec.

8.8.3. LVEF

Absolute change from baseline in LVEF will be summarized in the worst case post-baseline only. Only the post-baseline assessments that used the same method (e.g. ECHO) as the baseline assessments will be used to derive the change from baseline. The change from baseline will be categorized as follows:

- No change or any increase
- Any decrease
- >0-<10 decrease
- 10-19 decrease
- >=20 decrease
- >=10 decrease and >= LLN
- >=10 decrease and < LLN
- >=20 decrease and >= LLN
- >=20 decrease and < LLN

8.8.4. Anti-Drug Antibody analyses

For each subject, the anti-GSK2857916 (drug) antibody results, titers, and neutralizing antibody assay results, and also ADC and total antibody concentration will be listed for each assessment time point. The frequency and percentage of subjects with positive and negative anti-drug antibody and neutralizing antibody assay results will be summarized for each assessment time and overall for each subject by dose cohort. The conclusive results will be based on the total antibody concentration.

9. PHARMACOKINETIC ANALYSES

The pharmacokinetic analyses will be based on the “Full Pharmacokinetic” population.

Concentration-time data collected in Cycles 1 and 3 under protocol amendment 2 were analysed using standard non-compartmental (NCA) methods at the time of primary analyses. Some parameters were determined for all participants and cycles. The concentration-time data may be combined with data from other studies and will be analysed in a population approach using nonlinear mixed effects modelling. Full details are presented in [Appendix 13: List of Data Displays](#).

9.1. Drug Concentration Measures

Refer to [Appendix 5: Data Display Standards & Handling Conventions \(Section 15.5.3 Reporting Standards for Pharmacokinetic Parameters\)](#)

9.1.1. Non-compartmental Analysis

- Pharmacokinetic parameters described in [Table 6](#) below, were determined separately for each analyte, as data permitted.
- The pharmacokinetic parameters in Cycles 1 and 3 under protocol amendment 2 or later were calculated by standard non-compartmental analysis according to current working practices and using Phoenix WinNonlin, version 6.3 or later, as data permitted.
- The pharmacokinetic parameters C-EOI and Ctrough were determined directly from the concentration-time dataset for the other cycles under protocol amendment 2 and for participants enrolled prior to protocol amendment 2, as data permitted. Note: For the dosing occasions with only predose and end of infusion samples, the end of infusion concentration (C-EOI) was not identified as Cmax.
- All calculations of non-compartmental parameters were based on actual sampling times.

Table 6 Derived Pharmacokinetic Parameters

Parameter	Parameter Description
AUC(0-t)	Area under the concentration-time curve from time zero to the time of the last quantifiable concentration (C(t)) will be calculated using the linear trapezoidal rule for each incremental trapezoid and the log trapezoidal rule for each decremental trapezoid
AUC(0-t')	Area under the concentration-time curve to a fixed time t'
AUC(0-τ)	Area under the concentration-time curve during the dosing interval
AUC(0-∞)	Area under the concentration-time curve extrapolated to infinity will be calculated as: AUC = AUC(0-t) + C(t) / lambda_z
%AUC _{ex}	The percentage of AUC (0-∞) obtained by extrapolation (%AUC _{ex}) will be calculated as: [AUC(0-inf) – AUC(0-t)] / AUC(0-inf) x 100
C _{max}	Maximum observed concentration, determined directly from the concentration-time data for each cycle. C _{max} will not be derived when only predose and EOI samples were collected.
t _{max}	Time to reach C _{max} , determined directly from the concentration-time data for each cycle
C _τ	Trough concentration prior to the next dose for each cycle

Parameter	Parameter Description
Ctrough	
C-EOI	Observed plasma concentration at the end of infusion
t _{1/2}	Apparent terminal half-life will be calculated as: $t_{1/2} = \ln(2) / \lambda_{z}$
t _{last}	Time of last observed quantifiable concentration
CL	Clearance
V _{ss}	Volume of distribution at steady state
λ _z , λ _z	Terminal phase rate constant

9.2. Population of Interest

The pharmacokinetic (PK) analyses will be based on the ‘Full Pharmacokinetic’ population as defined in Section 4, unless otherwise specified.

9.3. Statistical Analyses / Methods

Details of the planned displays are provided in [Appendix 13](#): List of Data Display, based on GSK data standards and statistical principles. Unless otherwise specified, endpoints / variables defined in Section 9.1.1 will be summarised using descriptive statistics, graphically presented (where appropriate) and listed.

9.3.1. Statistical Methodology Specification

The following pharmacokinetic statistical analyses were performed when sufficient data were available.

9.3.1.1. Assessment of Accumulation Ratio

To assess the extent of accumulation following GSK2857916 repeat dosing, the observed accumulation ratio (Ro) for GSK2857916, total antibody, and cys-mcMMAF were determined as ratio of AUC and C_{max} at Cycle 3 to AUC and C_{max} at Cycle 1, respectively, using the data collected under protocol amendment 2. The same AUC parameter [AUC(0-t_{1/2}) or AUC(0-τ)] were used on the two occasions for each analyte, but analytes may have used different AUC parameters depending upon the data.

Participants must have received the same dose without delay or change for Cycles 1, 2, and 3 to be included in this analysis (i.e., with dosing delays of ≤3 days).

$$Ro(AUC) = AUC\ C3 / AUC\ C1;$$

AUC is AUC(0-τ) or AUC(0-t_{1/2})

$$Ro(C_{max}) = C_{max}\ C3 / C_{max}\ C1$$

Accumulation ratios of AUC and C_{max} were summarised using descriptive statistics by planned initial dose level, graphically presented (where appropriate) and listed.

An exploratory analysis was not performed considering the effect of dose delay or change on the ratio.

10. POPULATION PHARMACOKINETIC (POPPK) ANALYSES

Plasma GSK2857916 concentration-time data may be combined with data from other studies and will be analysed using a population pharmacokinetic approach. Details of the population PK analyses will be reported under a separate RAP, and the results of this analysis will be provided in a separate report.

11. PHARMACODYNAMIC AND BIOMARKER ANALYSES

If data permit, the relationship between clinical response and other biologic characteristics including BCMA expression on tumour cells and sBCMA concentrations may be explored. Details of these analyses will be specified within a separate biomarker RAP, and the results of these analysis will be provided in a separate report.

12. PHARMACOKINETIC / PHARMACODYNAMIC ANALYSES

12.1. Exposure-Response for Efficacy and Safety Endpoints

If deemed appropriate and if data permit, exposure-response relationships between GSK2857916 exposure (e.g., dose, dose intensity, concentration, C_{max}, or AUC) and clinical activity and/or toxicity (e.g., response, corneal event, AESIs) may be explored using population methods. If data permit, the effects of covariates may be explored. Details of these analyses will be reported under a separate RAP, and the results of this analysis will be provided in a separate report.

12.2. Concentration-QTc Analyses

Concentration-QTc Analyses were performed at the time of the primary analyses. For each ECG assessment, the individual subject's QTcF change from baseline were calculated and were merged with time-matched PK concentration values for the timepoints at which they are available. QTcF change from baseline (y-axis) were plotted against the PK concentration data (x-axis) separately for each analyte (ADC, total mAb, and cys-mc-MMAF). Linear regression analyses were performed for each analyte- Δ QTcF plot.

13. HEALTH OUTCOMES ANALYSIS

The EORTC QLQ-C30 (version 3.0), EORTC QLQ-MY20, and the PRO-CTCAE are three oncology-specific Health-Related Quality-of-Life (HRQoL) assessments that will be analysed in this study.

In addition, the impact of potential corneal event on function and health-related quality-of-life will be assessed with the use of two visual function questionnaires, the NEI-VFQ-25 and Ocular Surface Disease Index (OSDI).

The analysis population for EORTC QLQ-C30 and EORTC QLQ-MY20 will follow the rule for efficacy analysis, while the analysis population for PRO-CTCAE, NEI-VFQ-25, and OSDI will follow the rule for safety analysis.

13.1. European Organization for Research and Treatment of Cancer Quality of Life Questionnaire 30-item Core module (EORTC QLQ-C30)

The EORTC QLQ-C30 is a 30-item questionnaire containing both single- and multi-item measures [Aronson, 1993]. Details of deriving domain scores (9 scales and 6 single items) and summary score can be found in Section 15.11.1.

For summary score and each of domain scores, the following outputs will be provided:

- The descriptive summary of the actual value and change from baseline by visit.
- The number (%) of patients with improvement in score ≥ 10 , and ≥ 5 points respectively by visit.

13.2. European Organization for Research and Treatment of Cancer Quality of Life Questionnaire 20-item Multiple Myeloma module (EORTC QLQ-MY20)

The EORTC QLQ-MY20 is a supplement to the QLQ-C30 instrument used in patients with multiple myeloma [Aronson, 1993; Cocks, 2007]. The module comprises 20 questions that address four myeloma-specific HRQoL domains: Disease Symptoms, Side Effects of Treatment, Future Perspective, and Body Image. Three of the four QLQ-MY20 domains are multi-item scales: Disease Symptoms (includes bone aches or pain, back pain, hip pain, arm or shoulder pain, chest pain, and pain increasing with activity); Side Effects of Treatment (includes drowsiness, thirst, feeling ill, dry mouth, hair loss, upset by hair loss, tingling hands or feet, restlessness/agitation, acid indigestion/heartburn, and burning or sore eyes); and Future Perspective (includes worry about death and health in the future, and thinking about illness). The Body Image scale is a single-item scale that addresses physical attractiveness. Details of deriving domain scores can be found in Section 15.11.2.

For each of four domain scores, the following outputs will be provided:

- The descriptive summary of the actual value and change from baseline by visit
- Summary of the number (%) of patients with improvement in score ≥ 10 , and ≥ 5 points respectively by visit.

13.3. Patient-Reported Outcome Version of the Common Term Criteria for Adverse Events (PRO-CTCAE)

The Patient-Reported Outcomes Version of the Common Terminology Criteria for Adverse Events (PRO-CTCAE) is a patient-reported outcome measure developed to evaluate symptomatic toxicity in patients on cancer clinical trials [Basch, 2014]. The PRO-CTCAE was designed to be used as a companion to the Common Terminology Criteria for Adverse Events (CTCAE), the standard lexicon for adverse event reporting in cancer trials. The PRO-CTCAE includes an item library of 124 items representing 78 symptomatic toxicities drawn from the CTCAE. PRO-CTCAE provides a systematic yet flexible tool for descriptive reporting of symptomatic treatment side effects in cancer clinical trials. The levels and related code values for PRO-CTCAE are shown below.

	Levels and related code values				
Response scale	0	1	2	3	4
Frequency	Never	Rarely	Occasionally	Frequently	Almost Constantly
Severity	None	Mild	Moderate	Severe	Very severe
Interference	Not at all	A little bit	Somewhat	Quite a bit	Very much
Present/Absence	No	Yes			

For each selected item from the library: proportion of PRO-CTCAE scores for each item attribute (frequency, severity and/or interference) will be presented-with stacked bar charts by visit. Maximum PRO-CTCAE score at post-baseline for each item attribute will be summarized by counts and proportions. Proportion of patients with a maximum score of 3 or 4 for each item attribute (severe or very severe, frequently or almost constantly, quite a bit or very much) will also be reported. Proportions will be based on the number of patients with available data and subject with missing response will be excluded from analysis.

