5.2. Baseline Definitions

For all endpoints (except as noted in baseline definitions) the baseline value will be the latest pre-dose assessment with a non-missing value, including those from unscheduled visits. If time is not collected, Day 1 assessments are assumed to be taken prior to first dose and used as baseline. For subjects who did not receive study treatment during the study, baseline will be defined as the latest, non-missing collected value.

For laboratory data, baseline will be the latest non-missing pre-dose value from central lab. If no central lab value is available, the latest non-missing pre-dose value from local lab will be used.

For ECG analyses, subject level baseline is defined as the mean of triplicate baseline assessments.

Unless otherwise stated, if baseline data is missing, no derivation will be performed, and baseline will be set to missing.

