15.13.13. Health Outcomes Tables

Health Outcomes: Tables					
No.	Population	IDSL / Example Shell	Title	Programming Notes	Deliverable [Priority]
EORTC QLQ-C30					
8.0010	Full Analysis	Mock-up PRO_T1	Summary of Change in EORTC QLQ-C30 Summary Score from Baseline	Timepoints includes EOT visit	SAC [1], SAC [2]
8.0020	Full Analysis	Mock-up PRO_T1	Summary of Change in EORTC QLQ-C30 Domain Scores from Baseline	Including score for 15 domains. Timepoints includes EOT visit	SAC [1], SAC [2]
8.0030	Full Analysis	Mock-up PRO_T2	Number (%) of Subjects with Improvement in EORTC QLQ-C30 Summary Score \geq 10 by Visit	Timepoints includes EOT visit	SAC [1]
8.0040	Full Analysis	Mock-up PRO_T2	Number (%) of Subjects with Improvement in EORTC QLQ-C30 Domain Score \geq 10 by Visit	Including score for 15 domains. Timepoints includes EOT visit	SAC [1]
8.0050	Full Analysis	Mock-up PRO_T2	Number (%) of Subjects with Improvement in EORTC QLQ-C30 Summary Score \geq 5 by Visit	Timepoints includes EOT visit	SAC [1]
8.0060	Full Analysis	Mock-up PRO_T2	Number (%) of Subjects with Improvement in EORTC QLQ-C30 Domain Score \geq 5 by Visit	Including score for 15 domains. Timepoints includes EOT visit	SAC [1]
EORTC QLQ-MY20					
8.0070	Full Analysis	Mock-up PRO_T1	Summary of Change in EORTC QLQ-MY20 Domain Scores from Baseline	Timepoints includes EOT visit. Including score from 4 domains	SAC [1], SAC [2]
8.0080	Full Analysis	Mock-up PRO_T2	Number (%) of Subjects with Improvement in EORTC QLQ-MY20 Domain Scores \geq 10 by Visit	Pending on the availability of MID; Timepoints includes EOT visit Including score for 4 domains	SAC [1]
8.0081	Full Analysis	Mock-up PRO_T2	Number (%) of Subjects with Improvement in EORTC QLQ-MY20 Domain Scores \geq 5 by Visit	Pending on the availability of MID; Timepoints includes EOT visit Including score for 4 domains	SAC [1]

Health Outcomes: Tables					
No.	Population	IDSL / Example Shell	Title	Programming Notes	Deliverable [Priority]
PRO-CTCAE					
8.0090	Full Safety	Mock-up PRO_T3	Summary of Maximum Post-Baseline PRO-CTCAE Score	For each selected item from PRO-CTCAE library: create summary table for maximum post-baseline PRO-CTCAE score for each of 3 attributes (frequency, severity and/or interference).	SAC [1], SAC [2]
NEI-VFQ-25					
8.0100	Full Safety	Mock-up PRO_T1	Summary of Change in NEI-VFQ-25 Overall Composite Scores from Baseline	Timepoints includes EOT visit, last follow-up visit, and worst change from baseline.	SAC [1], SAC [2]

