Week x	n	xxx	xxx
	summary score/domain scores \geq 5/10/MID	xxx (xx%)	xxx (xx%)

Example: PRO_T3
 Protocol: 205678
 Population: Safety

Page 1 of 1
 (Data as of: 30MAY2001)

Table x.xxxx

Summary of maximum post-baseline PRO-CTCAE score

	Treatment Group A (N=xxx)			Treatment Group B (N=xxx)		
	Frequency	Severity	Interference	Frequency	Severity	Interference
Item x	n=xxx	n=xxx	n=xxx	n=xxx	n=xxx	n=xxx
Response						
0	xx (xx%)	xx (xx%)	xx (xx%)	xx (xx%)	xx (xx%)	xx (xx%)
1	xx (xx%)	xx (xx%)	xx (xx%)	xx (xx%)	xx (xx%)	xx (xx%)
2	xx (xx%)	xx (xx%)	xx (xx%)	xx (xx%)	xx (xx%)	xx (xx%)
3	xx (xx%)	xx (xx%)	xx (xx%)	xx (xx%)	xx (xx%)	xx (xx%)
4	xx (xx%)	xx (xx%)	xx (xx%)	xx (xx%)	xx (xx%)	xx (xx%)
3+4	xx (xx%)	xx (xx%)	xx (xx%)	xx (xx%)	xx (xx%)	xx (xx%)
Any Scale >0	xx (xx%)	xx (xx%)	xx (xx%)	xx (xx%)	xx (xx%)	xx (xx%)
Item y	n=xxx	n=xxx	n=xxx	n=xxx	n=xxx	n=xxx
Response Scale						
0	xx (xx%)	xx (xx%)	xx (xx%)	xx (xx%)	xx (xx%)	xx (xx%)
1	xx (xx%)	xx (xx%)	xx (xx%)	xx (xx%)	xx (xx%)	xx (xx%)
2	xx (xx%)	xx (xx%)	xx (xx%)	xx (xx%)	xx (xx%)	xx (xx%)
3	xx (xx%)	xx (xx%)	xx (xx%)	xx (xx%)	xx (xx%)	xx (xx%)
4	xx (xx%)	xx (xx%)	xx (xx%)	xx (xx%)	xx (xx%)	xx (xx%)
3+4	xx (xx%)	xx (xx%)	xx (xx%)	xx (xx%)	xx (xx%)	xx (xx%)
Any Scale >0	xx (xx%)	xx (xx%)	xx (xx%)	xx (xx%)	xx (xx%)	xx (xx%)

Note: For frequency levels, response scale stands for: 0-Never, 1-Rarely, 2-Occasionally, 3-Frequently, 4-Almost Constantly; for severity levels, response scale stands for: 0-None, 1-Mild, 2-Moderate, 3-Severe, 4-Very severe; for interference levels, response scale stands for: 0-Not at all, 1-A little bit, 2-Somewhat, 3-Quite a bit, 4-Very much.

Note: n1-n3 are the number of participants with at least one post-baseline response scale of the three attributes for a given item, which are used as denominator for calculation of percentage.

Example: PRO_T4
 Protocol: 205678
 Population: ITT

Page 1 of 1
 (Data as of: 30MAY2001)

Table x.xxxx

Summary of Worst Change from Baseline in NEI-VFQ-25 Overall Composite Score by Worst Grade of Corneal Event (GSK Scale)

		Frozen Liquid (2.5 + 3.4 mg/kg) + Lyo (3.4 mg/kg)			
		Worst Grade = 0	Worst Grade = 1,2	Worst Grade = 3,4	
		(N=xxx)	(N=xxx)	(N=xxx)	
Baseline	Actual Score	n	xx	xx	xx
		Mean	x.x	x.x	x.x
		SD	x.xx	x.xx	x.xx
		Median	x.x	x.x	x.x
		Min	x.x	x.x	x.x
		Max	xx.x	xx.x	xx.x
Worst Post-baseline	Actual Score	n	xx	xx	xx
		Mean	x.x	x.x	x.x
		SD	x.xx	x.xx	x.xx
		Median	x.x	x.x	x.x
		Min	x.x	x.x	x.x
		Max	xx.x	xx.x	xx.x

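### The PRO-CTCAE table reports only the raw post-baseline maximum, so unchanged pre-dose symptoms cannot be told apart from new or worsened ones

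*SAP*

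**What the plan says.** For each selected item, SAP Section 13.3 plans three summaries. Score distributions "will be presented-with stacked bar charts by visit". Then: "Maximum PRO-CTCAE score at post-baseline for each item attribute will be summarized by counts and proportions". The third output is the "Proportion of patients with a maximum score of 3 or 4 for each item attribute". Neither the second nor the third refers to the score before dosing.

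Table 8.0090 (Section 15.13.13) repeats the maximum-score summary. Its shell PRO_T3 (Section 15.14), titled "Summary of maximum post-baseline PRO-CTCAE score", has rows for scores 0 to 4, for 3 and 4 combined, and for any score above 0. It has no baseline block. The footnote sets the denominator: "n1-n3 are the number of participants with at least one post-baseline response scale of the three attributes for a given item". A baseline response is not needed to enter the table.

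Section 2.2 places PRO-CTCAE under the secondary objective on self-reported symptomatic adverse effects and tolerability. Section 5.2 already defines a baseline for all endpoints, with noted exceptions: "the baseline value will be the latest pre-dose assessment with a non-missing value". For gradable laboratory tests, Section 8.7 uses it: "These summaries will display the number and percentage of subjects with a maximum post-baseline grade increasing from their baseline grade".

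**The concern.** The objective concerns adverse effects, but the planned proportions mix two groups: participants whose symptom appeared or worsened on treatment, and participants who brought it with them. The study title in Section 14 describes people with three or more prior lines, refractory to two drug classes and with a failed anti-CD38 antibody, so symptoms at entry are plausible. Every cohort receives the study drug (Section 2.3), so no control arm shows the background rate. The participant's own baseline is the only internal reference, and the table does not use it.

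At stake is how the absolute tolerability rates are read. No hypothesis test or decision rule depends on this table.

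**Working it through.** **No figure to reproduce.** The SAP states no PRO-CTCAE rate, so the check is a reading of the displays plus an illustration.

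**Step 1. The five instruments side by side.**

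| Instrument | SAP section | Baseline comparison planned |
|---|---|---|
| QLQ-C30 | 13.1 | change from baseline by visit |
| QLQ-MY20 | 13.2 | change from baseline by visit |
| NEI-VFQ-25 | 13.4 | change from baseline by visit, and worst change |
| OSDI | 13.5 | change from baseline over time, and worst change |
| PRO-CTCAE | 13.3 | none |

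Shells PRO_T1 and PRO_T4 carry a baseline block; PRO_T3 does not.

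**Step 2. Three participants passed through PRO_T3.**

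| Baseline score | Post-baseline maximum | Row in PRO_T3 | Exceeds own baseline? |
|---|---|---|---|
| 0 | 3 | 3 and 4 combined | yes |
| 3 | 3 | 3 and 4 combined | no |
| 4 | 3 | 3 and 4 combined | no (improved) |

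The table treats all three alike.

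**Step 3. The difference between the two proportions.** A participant counts in the raw 3-or-4 proportion but not in a worsened-from-baseline version only if the maximum is 3 or 4 and does not exceed baseline. The baseline must then also have been 3 or 4. The excess therefore cannot be larger than the share at 3 or 4 before dosing.

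**Step 4. Illustration.** Let b be the share at 3 or 4 at baseline whose score does not change, and t the share of the remainder who newly reach 3 or 4. Both are assumptions.

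- Raw proportion = b + (1 − b)t
- Worsened-from-baseline proportion = (1 − b)t
- Difference = b

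For b = 20% and t = 20%: raw = 0.20 + 0.80 × 0.20 = 36%; worsened = 0.80 × 0.20 = 16%; difference = 20 points.

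| b | t = 0: raw / worsened | t = 10%: raw / worsened | t = 20%: raw / worsened |
|---|---|---|---|
| 5% | 5% / 0% | 14.5% / 9.5% | 24% / 19% |
| 10% | 10% / 0% | 19% / 9% | 28% / 18% |
| 20% | 20% / 0% | 28% / 8% | 36% / 16% |
| 30% | 30% / 0% | 37% / 7% | 44% / 14% |

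The row for any score above 0 behaves in the same way. If 50% had some symptom at baseline that stayed unchanged and t = 20%, the row would show 60%, of which 10% is new.

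**The case against.** Much of the case on the other side stands.

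- A reader might infer that PRO-CTCAE is the one place where this SAP ignores baseline. It is not. Worst post-baseline corneal events (Section 8.2.3, item 6), intraocular pressure of at least 22 mm Hg at any time post-baseline, and Descemet's folds or endothelial lesions at any post-baseline exam (Section 8.5) are also raw. The contrast holds only among the patient-reported instruments.
- A reader might infer that the SAP classes pre-dose symptoms as drug toxicity. It does not. Section 13.3 speaks of descriptive reporting, the table title is accurate, and no score is labelled drug-related.
- Baseline may be visible elsewhere. The by-visit bars (Figure 8.0010) are not restricted to post-baseline visits, and Listing 30.0270 gives responses by visit date. The figure image is not available, so this cannot be settled. Either display would give context, but as raw scores; neither would correct the maximum or the 3-or-4 proportion.
- The two frozen-liquid arms are randomized, so baseline burden is balanced in expectation and the dose contrast is not systematically biased. Any overstatement of absolute rates is in the cautious direction for safety.
- Baseline adjustment has its own defects. It does not separate drug effect from progressing myeloma. A participant at 4 before dosing can never count as worsened. Showing non-worsening as 0 could present a persistent severe symptom as none. With b = 30% and t = 20%, the worsened proportion is 14% although 20% of those able to reach 3 or 4 newly did so.

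These points rule out replacing the raw maximum. They do not remove the reason for showing baseline and worsening beside it.

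**Conclusion.** The point holds as a limited improvement to a descriptive display. Section 13.3, Table 8.0090 and PRO_T3 give symptom prevalence after dosing, and as prevalence the figures are sound. They do not show how much is new or worsened. If read that way, they are too high by the share already at 3 or 4 before dosing that remains there without worsening. That share cannot be found from the SAP; the 5 to 30 points in the illustration rest wholly on the assumed b and on unchanged baseline scores. The documents do not support the stronger conclusions that the table is invalid or that tolerability has been misclassified. Type I error and the primary response analysis are unaffected.

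**What to change.** Keep the raw maximum and its 3-or-4 proportion in PRO_T3 and Table 8.0090. Add, for each item attribute:

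1. the baseline score distribution, using the Section 5.2 definition;
2. the baseline-adjusted maximum, meaning the post-baseline maximum counted only if it exceeds the participant's own baseline score, with its 3-or-4 proportion;
3. a label stating that participants who did not worsen are not necessarily free of the symptom.

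Participants without a baseline score should appear only in the raw version, and the denominator of each column should be shown. The laboratory convention in Section 8.7, where a missing baseline grade is taken as 0, should not be carried over, because any reported symptom would then count as worsening. Section 13.3 needs a matching sentence.

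The cost is one derivation and some extra columns, with no new data collection. Table 8.0090 is listed for the end-of-study delivery as well as the primary analysis, so the change can be made there. The remaining downsides are that a baseline score of 4 cannot worsen and that the adjusted figure still includes symptoms that worsen through disease progression.
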